The efficacy of extended-release (ER) levomilnacipran has been established for major depressive disorder (MDD) in doses ranging from 40 mg/day to 120 mg/day (Sambunaris et al, 2014; Asnis et al, 2013). Levomilnacipran is the most noradrenergically active of the SNRI class of antidepressant drugs. Levomilnacipran was found to have twofold greater potency for norepinephrine relative to serotonin reuptake inhibition, and 17 and 27 times higher selectivity for norepinephrine reuptake inhibition compared with venlafaxine and duloxetine, respectively (Auclair et al, 2013).

Cognitive dysfunction in MDD is common and associated with greater impairment in functioning and quality of life. Given the similarities in mechanisms of action, it is possible for levomilnacipran to have beneficial effects on neurocognition. Apathy is considered a disorder of motivation and can occur in neuropsychiatric syndromes as well as depression. It is associated with neurocognitive disturbances and functional impairment. It remains understudied in depression.

Augmentation by adjunctive atypical antipsychotics is recommended as one of the clinical strategies on par with antidepressant switch in the APA guidelines to treat MDD. Quetiapine (extended release) is an atypical antipsychotic approved as adjunct to antidepressants for treatment of MDD in doses between 150-300 mg/day and has been extensively used in clinical practice.

Needs assessment: There is a significant unmet clinical need in terms of patients with MDD who show inadequate response and remission with SSRI treatment. Scientific evidence that guides appropriate treatment strategies in terms of further steps of switching or augmentation of medications will improve clinical care in patients with MDD who do not show adequate response to SSRIs.

II. STUDY OBJECTIVE(S):

Primary:

1. To compare the efficacy and tolerability of switching to levomilnacipran ER (40-120 mg/d) versus augmentation with quetiapine 150-300 mg/day to the patients' existing treatment for patients with inadequate relief on generic SSRIs in patients with MDD.

Secondary:

1. To examine the response and remission rates following the switch from generic SSRI to levomilnacipran ER and augmentation with quetiapine.
2. To examine changes in neurocognitive and apathy measures after switching from SSRI to levomilnacipran and after augmentation with quetiapine in MDD

III. STUDY DESIGN and PLAN:

Methodology:

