This is an 8-week, randomized rater blinded parallel group, 2-arm trial to comparing a switch to levomilnacipran ER versus augmentation with quetiapine.

Participants who meet inclusion/exclusion criteria for inadequate response to existing antidepressants will be randomly assigned (1:1 ratio) to either levomilnacipran ER or augmentation with quetiapine and their existing antidepressants in the same dose for 8 weeks. A flexible dose regime of levomilnacipran ER 40-120 mg/d mg per day will be employed with titrating doses starting at 20 mg/d on Days 1-2, increasing to 40 mg/d on Days 3-7 in week 1, then flexibly dosed between 40 mg/d -120 mg/d during weeks 2 through 8. FDA approved package insert guidelines will be followed for the adjunctive

quetiapine dosing. Quetiapine will be started at 50 mg/d on Day 1-2, increasing to 150 mg/d on Days 3-7 in Week 1 and then flexibly dosed between 150-300 mg/d during Weeks 1 through 8 along with their current antidepressant. Patients who cannot tolerate the higher dose of levomilnacipran ER or quetiapine will have their dose reduced to a lower dose per the investigator's judgment. The primary efficacy measure rating will be performed by a blinded rater.

IV. STUDY POPULATION:

- A. A total of 60 subjects (n=30 in each group) will be studied at 2 sites. A total of 40 subjects will be screened for a total of 30 eligible subjects to be enrolled at Duke.
- B. Potential participants will be identified by self-referral via the printed ad, phone Script, the patients' physicians, local health providers, mental health providers, or Duke providers; if not self-referred, the potential participant will have the study introduced by a care provider known to them as meeting the inclusion criteria will be offered basic information about the protocol by the PI or Study Coordinator and if interested, provided with an appointment for the purposes of obtaining informed consent and screening assessments.

During the phone screen interview the study coordinator will collect specific protected health information (PHI) for ascertaining subject eligibility and to determine if an appointment should be set up. If the is ineligible to participate or decides not to participate in the study, the PHI will be destroyed. The PI or Study Coordinator will also clearly explain to them that a refusal to participate in the study will not affect their participation to treatment at their regular treating physician or Duke University Medical Center (DUMC).

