- Has a disease or takes medication that, in the opinion of the investigator, could interfere with the assessments of safety, tolerability, or efficacy or prevent the individual from completing the study. Female subjects of childbearing potential not on adequate contraception methods in the opinion of the investigator
 - If the female is childbearing, she must agree to use appropriate contraceptive measures for the duration of the study and for one month afterwards. Medically acceptable contraceptives include: (1) surgical sterilization (such as tubal ligation or hysterectomy), (2) approved hormonal contraceptives (such as birth control pills, patches, implants, or injections), (3) barrier methods (such as condom or diaphragm) used with a spermicide, or (4) an intrauterine device (IUD). Contraceptive measures such as Plan B™, sold for emergency use after unprotected sex, are not acceptable methods for routine use. If the female does become pregnant during this study she must inform the study physician immediately.
- Has a significant risk of suicide according to Columbia Suicide Severity Rating Scale (CSSRS) or in the clinical judgment of the investigator
- History of suicide attempt in the previous 12 months
- MDD with postpartum onset, psychotic features or seasonal features
- Hamilton Anxiety Scale (HAM-A) baseline score ≥ 24
- Failure of ≥ 3 adequate trials of different antidepressants for the current episode of MDD
- ≥ 3 episodes major depression in previous 12 months or ≥ 8 lifetime episodes of MDD
- Current or previous use of an atypical or typical antipsychotic agent for augmentation of major depression or treatment of psychotic depression, mania psychosis, or agitation. Previous use of antipsychotics for insomnia will be permitted.

V. STUDY PROCEDURES

A. Blinding and Controls:

The study will be rater blinded, randomized, parallel study. Patients will be randomized in 1:1 ratio to levomilnacipran ER switch arm or adjunctive quetiapine arm. Subjects will be instructed not to discuss any clinical issue with the blinded rater. The blinded rater will be specifically instructed to perform specified ratings only and not to address or ask any other study related questions.

B. Drugs, Dosages, and Regimens:

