radiology reports, progress notes, hospital admission and emergency room notes, holding and observation notes, discharge summaries, autopsy reports, and death certificates.

Reporting of Pregnancy to Allergan, Inc. / Forest Research Institute

Study center personnel will report every pregnancy on a pregnancy report form as soon as possible (within 24 hours of first awareness of the pregnancy to the Allergan, Inc. pregnancy fax number, [contact]), even if no AE has occurred, and follow it to term. If, however, the pregnancy is associated with an SAE (e.g., if the mother is hospitalized for dehydration), in addition to the pregnancy report form, a separate SAE report form will be filed.

Any Serious Adverse Event will also be reported to the Duke IRB, to the FDA within 24 hours. The FDA Adverse Event Reporting System (AERS) is a computerized information database designed to support the FDA's post-marketing safety surveillance program for all approved drug and therapeutic biologic products. The FDA uses AERS to monitor for new adverse events and medication errors that might occur with these marketed products.

VII. STATISTICAL EVALUATION

A. Power analysis:

The proposed design levomilnacipran switch has never previously been studied in either a randomized or open-label design. Thus no direct pilot data exist upon which to base a power analysis. As is recommended for cases where pilot data are absent or minimal, clinical trials can be powered to detect clinically meaningful effect sizes. What is clinically meaningful depends on the illness and outcome being studied. According to mainstream resources, such as British National Institute for Health and Clinical Excellence (NICE), it is generally accepted that small effect sizes are not clinically meaningful, while medium effect sizes are. If one uses standardized effect sizes (Cohen's d) to determine clinical significance, the British National Institute for Health and Clinical Excellence (NICE) has suggested that $d=0.50$ should be the standard general threshold for "clinical significance" in drug treatments (www.nice.org.uk). This standard has been applied to assessing efficacy in RCTs with antidepressants in MDD (Kirsch et al., 2008).

Sample Size calculations for two-sided log rank test in survival analysis

Power	Proportion Response: Drug	Proportion Response: Placebo	Alpha	Number in each group
0.90	.33	.17	0.05	44
0.80	.33	.17	0.05	28
0.90	.45	.27	0.05	48
0.80	.45	.27	0.05	31

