Using Cohen's d effect size to determine sample size, in Cohen's standard text on statistical power (Cohen, 1988), using the NICE definition of a $d=0.5$ or larger, we obtain an estimated sample size (given a two-sided $\alpha = 0.05$ and $1 - \text{Beta} = 0.800$) of $n= 30$ per arm or 60 for the study. A power analysis was also conducted based on an effect size estimate derived from the drug-placebo difference in primary outcome of MADRS scores in published levomilnacipran trials (Citrome, 2013). The summary of Least square mean change between drug and placebo at 95% CI was -4.9 ($p<.0001$). With a two-tailed $\alpha= 0.05$, a sample size of $n= 60$ provides a power of 0.80.

B. Randomization Method

Randomization will occur with randomly generated computer lists held at the Duke site. This group will assign subjects according to a computer-generated the randomization sequence (without blocking or stratification) for each site. After the study coordinator determines eligibility, the participant will be randomized to one of two different arms. Drug capsules will be placed in standard medicine bottles. Each bottle will be dispensed individually by the study coordinator at the appropriate visit. Rater unblinding will be done at the end of the study after data lock. In case of any AEs or SAEs or other emergencies that require the blind to be broken, the pharmacy will have a 24-hour on call support service.

Power analysis was performed using an internet based software program. The results showed that a sample size of $n=60$ ($n=20$ in each of the 3 groups) could detect a strong effect with $\alpha = .05$, unless the true mean difference is quite minimal.

C. Plan of Data analysis

Subjects will be defined as able to be evaluated by two methods. The primary method will be an intent-to-treat analysis, including those who discontinue drug due to lack of efficacy or due to side effects. The secondary method will be completer analysis. The intent-to-treat (ITT) group will include randomly assigned patients receiving study drug with a post baseline efficacy assessment. The safety population will comprise all patients receiving study drug with a post baseline safety assessment.

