Primary efficacy analysis will be conducted in the ITT population using the last-observation-carried-forward (LOCF) method. Treatment group comparisons will base on changes in MADRS from baseline to week 8/end of treatment from repeated measures ANOVA or analysis-of-covariance (ANCOVA) model containing treatment site, gender and baseline MADRS score included as a covariate.

Secondary efficacy analysis: Repeated measures ANOVA or ANCOVA models will be used to analyze change from baseline in secondary measures. Response and remission rates at end of treatment will be compared using the Cochran-Mantel- Haenszel test. No formal hypothesis testing will be performed on safety data. Safety outcomes will be summarized by treatment group and study visit (observed cases) using descriptive statistics. Any clinically significant findings among patients who terminated early will be discussed separately. All analyses will be conducted using SAS Version 9.1.3 (SAS Institute, Inc.; Cary, North Carolina). Statistical comparisons of efficacy outcomes will be 2-sided and considered significant at $P < .05$. Comparisons for secondary endpoints will be not adjusted for multiplicity.

D. Definition of Evaluable Subject (Safety and Efficacy)

Subjects will be defined as able to be evaluated by two methods. The primary method will be an intent-to-treat analysis, including those who discontinue drug due to lack of efficacy or due to side effects. The secondary method will be completer analysis.

XI: ETHICAL AND REGULATORY CONSIDERATIONS

A. Institutional Committee Approval

Duke University Health Systems Institutional Review Board (DUHS IRB) will need to approve the protocol at the Duke site. [name] site will use an external IRB (e.g. Copernicus, Western) and provide Duke with a copy of its approval.

B. Informed Consent

Participation in this study is voluntary and at no cost to the subjects. All potential participants interested in this study must be thoroughly informed of the details of the study. Prior to study participation in this trial, each subject will have an opportunity to ask questions and will sign an approved informed consent form. The signed consent forms will be filed with the investigator's copies of the Case Report Forms for each subject and a copy provided to the subject. Any subject may voluntarily withdraw from the study at any time without prejudicing treatment.

C. Document Storage and Retention

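### The log-rank sample-size table is about 3.2 to 4.2 times too small at 80% power, and it and the three-group power sentence describe a different design from this two-arm trial without placebo

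*Combined protocol and SAP*

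**What the plan says.** Design. Study Design and Plan states: "This is an 8-week, randomized rater blinded parallel group, 2-arm trial". Study Population gives the size: "A total of 60 subjects (n=30 in each group) will be studied at 2 sites". Blinding and Controls names the arms: "Patients will be randomized in 1:1 ratio to levomilnacipran ER switch arm or adjunctive quetiapine arm". Both arms are active; there is no placebo.

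Response. The first secondary objective is "To examine the response and remission rates following the switch from generic SSRI to levomilnacipran ER and augmentation with quetiapine". Under Plan of Data analysis, "Response and remission rates at end of treatment will be compared using the Cochran-Mantel- Haenszel test". The primary endpoint is change in MADRS total score. No time-to-event endpoint or log-rank analysis appears in the plan.

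Power. Statistical Evaluation, part A, contains a table headed "Sample Size calculations for two-sided log rank test in survival analysis", with response proportions for drug and placebo, alpha 0.05 and a number in each group:

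| Power | Drug | Placebo | Stated n per group |
|---|---|---|---|
| 0.90 | 0.33 | 0.17 | 44 |
| 0.80 | 0.33 | 0.17 | 28 |
| 0.90 | 0.45 | 0.27 | 48 |
| 0.80 | 0.45 | 0.27 | 31 |

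The text after the table derives 30 per arm from a standardized effect of 0.5 and also cites a MADRS difference of -4.9. Part B (Randomization Method) then adds that "a sample size of $n=60$ ($n=20$ in each of the 3 groups) could detect a strong effect" at alpha 0.05, "unless the true mean difference is quite minimal".

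**The concern.** Differences of 16 and 18 percentage points in response usually need more than 100 patients per group for 80% power, so 28 and 31 look far too small. The placebo column, the survival test and the three groups also do not belong to this trial.

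Response and remission are a stated objective and are formally tested. A reader who sees 28 and 31 at 80% power next to the planned 30 per arm will infer that the response comparison is adequately powered. If it is not, a non-significant result could be taken as evidence that switching and augmentation perform alike, when the trial was unlikely to show a difference of that size.

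**Working it through.** **Inputs.** Proportions, power, alpha and stated n come from the table; 30 per arm comes from Study Population. The documents give no accrual, hazard or dropout assumptions for the table. I assume proportional hazards, equal fixed follow-up and no dropout; dropout would raise every required n.

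**1. Log-rank size with response as the event.**

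HR = ln(1−p1)/ln(1−p2):
- 0.33 vs 0.17: ln(0.67)/ln(0.83) = 2.149
- 0.45 vs 0.27: ln(0.55)/ln(0.73) = 1.900

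Total events, with z = 1.960 + 0.842 at 80% power:
- Schoenfeld, 4z²/(ln HR)²: 53.6 and 76.3
- Freedman, z²[(HR+1)/(HR−1)]²: 58.9 and 81.5

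n per group = events/(p1+p2). For 0.33 vs 0.17 this is 53.6/0.50 = 107 to 58.9/0.50 = 118. For 0.45 vs 0.27 it is 76.3/0.72 = 106 to 81.5/0.72 = 113 (114 when rounded up).

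**2. All four rows.** The next-to-last column reads the proportions as event-free instead, which is the more lenient of the two readings.

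| Row | Stated n | Response as event | Proportion event-free | Needed / stated |
|---|---|---|---|---|
| 0.33 vs 0.17, 80% | 28 | 107–118 | 95–99 | 3.4–4.2 |
| 0.45 vs 0.27, 80% | 31 | 106–114 | 100–104 | 3.2–3.7 |
| 0.33 vs 0.17, 90% | 44 | 144–158 | 127–132 | 2.9–3.6 |
| 0.45 vs 0.27, 90% | 48 | 142–152 | 134–140 | 2.8–3.2 |

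A pooled two-proportion calculation gives 114 and 111 at 80% power, and 152 and 148 at 90%.

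**3. Attempts to reproduce the stated figures.**
- Two-sided events per group: 26.8–29.5 brackets 28, but the same reading gives 36–39 against 44, 38–41 against 31 and 51–55 against 48.
- One-sided events per group: 30.0–32.1 brackets 31, but the same reading gives 21–23 against 28.
- Proportions as hazards, every patient having an event: 36–38 against 28 and 60–63 against 31.
- One-sided log-rank n per group at 80%: 76–94 and 80–91.

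No single convention gives all four rows.

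**4. A check free of the effect size.** At fixed alpha, n(90%)/n(80%) = [(z_α+1.2816)/(z_α+0.8416)]². This is 1.34 for a two-sided 5% test and 1.39 for a one-sided test. The table has 44/28 = 1.57 and 48/31 = 1.55, and at least 1.51 after allowing for rounding. Ratios of 1.57 and 1.55 would need a two-sided alpha of about 0.37 and 0.34. The rows therefore contradict each other whatever hazard ratio or event rate is assumed.

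**5. Actual power for response.**
- At the table's own n, two-proportion power is 0.28 (28 per group, 0.33 vs 0.17) and 0.31 (31 per group, 0.45 vs 0.27), against the stated 0.80.
- At 30 per arm, exact enumeration of the chi-square/CMH statistic in one stratum gives 0.297 and 0.300.
- 80% power at 30 per arm needs about 0.51 vs 0.17 or 0.62 vs 0.27, a gap of 34–35 points rather than 16–18.
- 95% CI half-width: 1.96·√[(0.33·0.67+0.17·0.83)/30] = 0.215 and 1.96·√[(0.45·0.55+0.27·0.73)/30] = 0.239.

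**6. The three-group sentence.** Three groups of 20 have 78% power at f = 0.40, a conventionally large effect. Two groups of 30 (two-sided t-test) have 86% power at d = 0.8, 48% at d = 0.5 and 12% at d = 0.2; 80% power needs d of about 0.74. The claim about a strong effect is roughly right. The claim that only a minimal difference would be missed is not.

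**The case against.** The table does not set the sample size: 30 per arm is derived from an effect size of 0.5, and response is a secondary comparison. That stands. It limits the seriousness of the error but does not make the figures right.

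The multiplier depends on how the proportions are read. If they are hazards and every patient has an event, the 80% rows are short by only 1.3–1.4 and 1.9–2.0 times; read as events per group, by about 1.0 and 1.2–1.3 times. This stands as a condition on the size of the error. The columns are labelled as response proportions and numbers per group, no alternative gives all four rows, and the ratio check fails under every reading.

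The rates were for drug against placebo, so quoting power at those rates for two active arms borrows inputs that nothing in the plan supports. This is fair. The 30% figure corrects what the table claims; it does not forecast this comparison. The detectable difference and the interval width should therefore stand beside it.

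The d of 0.74 is for an unadjusted t-test, while the plan allows covariance adjustment for baseline MADRS. With an assumed baseline correlation of 0.5 (none is given), it would fall to 0.736·√(1−0.25) = 0.64, which is still not minimal.

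The plan states no equivalence or non-inferiority aim, so misreading a null result as similarity is a risk, not something the plan proposes.

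**Conclusion.** The concern holds. Under the labels as printed, with proportional hazards, common follow-up and no dropout, the 80% rows are about 3.2–4.2 times too small and the 90% rows about 2.8–3.6 times. The rows are also inconsistent with one another at any 5% alpha. The placebo comparator, the log-rank test and the three groups of 20 contradict the plan's own design of two active arms of 30 with a CMH comparison of response. At 30 per arm, power for the tabulated differences is about 30%, not about 80%. The correction should be made, but it affects the stated power for a secondary objective, not the analysis or the stated derivation of 60 patients.

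**What to change.** Delete the log-rank table and the three-group paragraph. In their place, state that with 30 per arm the planned response comparison has about 30% power for 0.33 vs 0.17 or 0.45 vs 0.27 (labelled as illustrative rates), that 80% power would need about 114 and 111 per arm respectively, and that 30 per arm gives 80% power only for a gap of about 34–35 points. Keep the prespecified CMH test, and also report the response and remission differences with 95% confidence intervals; for response the expected half-width at these rates is about 22–24 points.

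The cost is protocol and SAP text only. Enrolment, the primary analysis and the CMH test are unchanged, though the stated power for response becomes less favourable. This does not settle whether an effect size of 0.5 supports 30 per arm, which needs separate attention.

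### Thirty patients per arm does not give 80% power at d = 0.5: that needs 64 per arm, and the other sample-size statements do not support 60 in total

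*Combined protocol and SAP*

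**What the plan says.** All references are to the combined protocol and SAP.

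- **Section IV.A** sets the size: "A total of 60 subjects (n=30 in each group) will be studied at 2 sites". Sections III and V.A describe two active arms, randomised 1:1, without placebo.
- **Statistical Evaluation, A (Power analysis)** adopts d = 0.5 as the threshold for clinical significance. With two-sided alpha 0.05 and power 0.80 it arrives at a size "of $n= 30$ per arm or 60 for the study".
- **The same section** has a table headed "Sample Size calculations for two-sided log rank test in survival analysis". For drug against placebo it gives 28 (80% power) and 44 (90%) per group for response proportions .33 and .17, and 31 and 48 for .45 and .27.
- **The same section** adds a calculation from an "effect size estimate derived from the drug-placebo difference in primary outcome of MADRS scores in published levomilnacipran trials". The difference is 4.9 points, and n = 60 "provides a power of 0.80". No SD is given.
- **Statistical Evaluation, B (Randomization Method)** contains another power statement: 60 patients, 20 "in each of the 3 groups) could detect a strong effect with" alpha .05.
- **Statistical Evaluation, C (Plan of Data analysis)** names repeated measures ANOVA or ANCOVA for MADRS change, with site, "gender and baseline MADRS score included as a covariate". Response and remission are compared by a Cochran-Mantel-Haenszel test. The ITT set consists of "randomly assigned patients receiving study drug with a post baseline efficacy assessment", with LOCF.

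**The concern.** The d = 0.5 statement gives every input needed to check it, and 30 per arm is less than half of what a two-sample formula returns. The other three statements do not offer an independent route to 60: one is for a test and a comparator that this trial does not have, one is for a different number of groups, and one omits the SD.

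What is at stake is how the result will be read. The plan tells readers that the trial has an 80% chance of detecting the smallest difference it regards as clinically meaningful. If the true chance is near one half, a non-significant result could be mistaken for evidence that switching and augmentation perform alike.

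**Working it through.** **1. The main calculation.** Inputs from the Power analysis section: d = 0.5, two-sided alpha 0.05, power 0.80, two independent arms.

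Normal approximation: n per arm = 2(1.960 + 0.842)² / 0.5² = 62.8, so 63. With the non-central t it is 63.8, so **64 per arm** (power 0.801). The stated 30 is not reproduced.

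Other readings that might lead to 30:

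| Reading | Result |
|---|---|
| One-sided alpha | 51 per arm |
| 60 taken as per arm | power 0.775 |
| One-sample or paired formula | 32 (normal) or 34 (t) |

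The last comes close to 30, but it does not apply to two independent groups. The first two contradict the stated two-sided test and the stated 30 per group.

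**2. What 30 per arm delivers, unadjusted.** The non-centrality is 0.5 × √(30/2) = 1.94 on 58 df, so power is **0.478**. Power reaches 80% at d = **0.736**. With 27 or 24 evaluable per arm (10% or 20% not evaluable, assumed), power at d = 0.5 is 0.438 or 0.396.

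**3. The planned ANCOVA.** Replace d by d/√(1 − r²), where r is the correlation of baseline with the outcome whose SD defines d, and spend 3 df on site, gender and baseline. The documents give no r, so the values below are assumptions.

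| r | Power, 30/arm | 27/arm | 24/arm | n/arm for 80% |
|---|---|---|---|---|
| 0.3 | 0.514 | 0.471 | 0.427 | 59 |
| 0.5 | 0.594 | 0.548 | 0.498 | 49 |

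With 30 per arm, 80% at d = 0.5 needs r of about 0.73.

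**4. The log-rank table.** Events required are 4(1.960 + 0.842)²/(ln HR)² (Schoenfeld), or (1.960 + 0.842)²(HR + 1)²/(HR − 1)² (Freedman). Divide by the average event proportion for the total, then by 2 for each group. The table does not say whether its proportions are events or event-free patients, so both readings were tried.

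Example: .33 and .17 read as events give HR = ln(0.67)/ln(0.83) = 2.149. Schoenfeld then needs 53.6 events, and 53.6/0.25/2 = 107.3, so 108 per group.

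| Proportions | Power | Stated n/group | Recomputed, all variants |
|---|---|---|---|
| .33 / .17 | 80% | 28 | 96–118 |
| .33 / .17 | 90% | 44 | 128–158 |
| .45 / .27 | 80% | 31 | 101–114 |
| .45 / .27 | 90% | 48 | 135–153 |

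At the stated 28 and 31 per group, power is about 28–34%. The table is also inconsistent internally: for a fixed effect, going from 80% to 90% power multiplies n by 1.34, but 44/28 = 1.57 and 48/31 = 1.55.

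**5. The 4.9-point calculation.** If 60 is the total, 80% power needs an SD of at most 4.9/0.736 = 6.66. If 60 is per arm, the limit is 9.50. With 30 per arm and assumed SDs of 7, 8, 9 and 10, power is 0.76, 0.65, 0.55 and 0.46.

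**6. Precision.** The expected unadjusted 95% half-width is 2.002 × SD × √(2/30) = 0.517 SD. At assumed SDs of 8 and 10 that is 4.1 and 5.2 MADRS points. An observed difference of exactly 0.5 SD would therefore not be significant in the unadjusted comparison.

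**The case against.** The main figure has no good defence, but several of the surrounding numbers can be challenged.

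- **ANCOVA figures depend on a convention.** The primary outcome is change. If d is standardised by the SD of change, and r is the baseline–week 8 correlation with equal variances, the variance ratio is (1 + r)/2. Power at 30 per arm is then 0.66 at r = 0.3, 0.59 at r = 0.5 and 0.54 at r = 0.7. This stands: any ANCOVA figure must say what r and d refer to. It does not rescue the claim. The ratio needed for 80% is 1 − 0.734² = 0.461, which on this reading requires a negative r (2 × 0.461 − 1 = −0.08). The repeated measures alternative was not evaluated, because the plan gives no correlations for it.
- **The 10–20% loss has no source in the plan.** ITT entry needs only one post-baseline assessment, the first such visit is week 1, and later dropouts are carried forward. The loss from the primary analysis could be smaller, so the range must be labelled as an assumption. The 48% figure assumes no loss at all.
- **The 4.9-point calculation is not shown to be wrong.** It cannot be checked. The plan openly says it is a drug–placebo difference; the difficulty is that the trial compares two active strategies.
- **The log-rank table is itself a two-group table.** Its mismatch is the placebo comparator and the unplanned test, not the number of groups. The recomputed sizes depend on formula and reading, but every variant is more than three times the stated n at 80% power.

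**Conclusion.** The concern holds. On the plan's own inputs the required size is 64 per arm, not 30. The planned 60 patients give about 48% power at d = 0.5 unadjusted, which rests on nothing beyond the stated inputs and full evaluability. Baseline adjustment gives about 51–59% under the convention in the working, or up to 0.66 under the change-score convention, for assumed correlations of 0.3–0.5. None of these reaches 80%.

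No other statement in the plan supplies a valid basis for 60: the log-rank table and the three-group sentence do not belong to this design, and the 4.9-point calculation cannot be verified. This must be corrected, because it misstates what the primary comparison can show. It does not make a trial of 60 improper; it makes the claim about it wrong.

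**What to change.** Keep 60 patients and replace the 80% claim in the Power analysis section with wording such as:

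> With 30 evaluable patients per arm, an unadjusted two-sided 5% comparison has about 48% power at d = 0.5 and 80% power at d of about 0.74. If 10–20% of patients are not evaluable (an assumption), power at d = 0.5 is about 0.44–0.40.

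Then:

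- State the assumed MADRS SD, with its source, and the expected 95% confidence-interval half-width.
- If an ANCOVA power figure is quoted, give the assumed correlation and say whether it and d refer to the week 8 score or to change.
- Delete the log-rank table, and the three-group sentence under Randomization Method.
- Remove the 4.9-point calculation, or give its SD, say whether 60 is the total, and explain why a drug–placebo difference is relevant to two active strategies.

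This changes wording only and adds no patients; the price is a less favourable stated power. Keeping 80% at d = 0.5 instead would take 2 × 64 = 128 evaluable patients unadjusted, or 98–118 with ANCOVA (2 × 49 at r = 0.5, 2 × 59 at r = 0.3, under the convention in the working). Declaring d of about 0.74 as the target would also reconcile the arithmetic, but it would need its own justification, since the plan sets its clinical threshold at 0.5.

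### The 0.80 power claimed at n=60 rests on a 4.9-point levomilnacipran-placebo MADRS difference, but the primary test compares two active strategies, so the figure is unsupported for the comparison made

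*Combined protocol and SAP*

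**What the plan says.** Section III (Methodology) describes a "2-arm trial to comparing a switch to levomilnacipran ER versus augmentation with quetiapine", randomized 1:1 with 30 patients per arm. There is no placebo arm. Section VII.C (Plan of Data analysis) sets the primary comparison: "Treatment group comparisons will base on changes in MADRS from baseline to week 8/end of treatment". It adds that "Statistical comparisons of efficacy outcomes will be 2-sided and considered significant at $P < .05".

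Section VII.A (Power analysis) notes that no direct pilot data exist and first derives 30 per arm from a standardized effect of d=0.5. It then reports a second calculation, based on an "effect size estimate derived from the drug-placebo difference in primary outcome of MADRS scores in published levomilnacipran trials". The input is given as follows: "The summary of Least square mean change between drug and placebo at 95% CI was -4.9". The conclusion is: "With a two-tailed $\alpha= 0.05$, a sample size of $n= 60$ provides a power of 0.80". A table of response proportions in the same section has columns headed for drug and placebo.

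No section gives an expected difference between levomilnacipran and quetiapine, an SD for MADRS change, a dropout allowance or a non-inferiority margin.

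**The concern.** A power statement describes one contrast. The 4.9 points are the gap between levomilnacipran and placebo in other trials, whereas this trial tests the gap between levomilnacipran and an active comparator. The introduction itself describes that comparator as "approved as adjunct to antidepressants for treatment of MDD in doses between 150-300 mg/day and has been extensively used in clinical practice", and it ranks augmentation with atypical antipsychotics level with switching as a guideline strategy. Nothing in the plan explains why the full drug-placebo gap should be expected between two such strategies.

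The stake is how the result will be read. The trial is meant to inform the choice between switching and augmenting, and the primary test is a test of difference. If that test is not significant, a stated power of 0.80 makes the result look more informative than the design can support.

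**Working it through.** **Inputs from the document:** difference 4.9 MADRS points (drug versus placebo); 30 per arm, 1:1; two-sided alpha 0.05; stated power 0.80. **Not in the document, so assumed:** the SD of MADRS change and the true difference between the two arms.

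**Step 1: the plan's own figure.** Without an SD, the 0.80 can be neither confirmed nor refuted, but the SD that would make it true can be found. For a two-sample t-test with n per arm, power is the probability that a noncentral t variable with 2n - 2 = 58 degrees of freedom and noncentrality d × √(n/2) = d × √15 exceeds the two-sided 5% critical value of 2.00 in absolute size. Solving for power 0.80 gives d = 0.736, so SD = 4.9 / 0.736 = 6.66. The normal approximation, SD = 4.9 × √15 / (1.960 + 0.842), gives 6.77. The t-test value is used below. It is the reading most favourable to the claim, because it takes the 0.80 as correct at 4.9 points.

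**Step 2: power at other between-arm differences** (t-test, 30 per arm, all evaluable, no covariate adjustment).

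| True between-arm difference | SD 6.66 | SD 8 |
|---|---|---|
| 4.9 | 0.80 | 0.65 |
| 3.9 | 0.61 | 0.46 |
| 2.45 (half of 4.9) | 0.29 | 0.22 |

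The differences and SDs are illustrations, not estimates. Reaching 0.80 power for 2.45 points at SD 6.66 would take about 117 per arm.

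**Step 3: does the d=0.5 calculation support 0.80 instead?** It names no comparator, so the objection about the contrast does not reach it. Its arithmetic fails, however. At d=0.5 and 30 per arm, two-sided power is 0.48, and 0.80 power needs 64 per arm.

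**Step 4: what 30 per arm can detect.** At 0.80 power the detectable difference is 0.736 × SD:
- SD 6.66: 4.9 points
- SD 8: 5.9 points
- SD 10: 7.4 points

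Two features of the planned analysis move this. ANCOVA on baseline MADRS reduces it: with an assumed baseline correlation of 0.5, 0.736 × √(1 - 0.25) = 0.64 SD. Loss of patients increases it: with an assumed 24 evaluable per arm, it is 0.83 SD.

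**Step 5: precision.** The unadjusted 95% CI half-width is 2.00 × SD × √(2/30). That is 3.4 points at SD 6.66 and 5.2 points at SD 10.

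**The case against.** The strongest reply is that this is a supporting calculation. The sample size is first derived from d=0.5, and the 4.9-point analysis is presented as an additional one. That is correct and limits the point, but the d=0.5 derivation cannot carry the 0.80 either (Step 3).

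A second reply is that every figure below 0.80 depends on assumed values. This stands. A reader might subtract a quetiapine gain over placebo from 4.9 and treat the remainder as the expected difference. The document does not support that model. One arm tapers its SSRI while the other continues its antidepressant, so the two gains need not share a reference. The test is also two-sided, so a difference of 4.9 points or more, in either direction, is not excluded.

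A reader might also infer that a non-significant result is the likely outcome. The document does not show this. At SD 6.66, power stays above one half until the true difference falls to about 3.4 points, which is 1.5 points below 4.9.

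Finally, no section claims equivalence or says that a non-significant result will be read that way. The advice on interpretation is a safeguard, not the correction of a stated error.

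**Conclusion.** The point holds. The 0.80 belongs to a contrast that the trial does not test, and the plan offers no bridge from one contrast to the other. This does not depend on any SD: whichever value is supplied, 4.9 remains a drug-placebo figure.

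The size of the shortfall is unknown. At any fixed SD, a true between-arm difference smaller than 4.9 points has less power than the same calculation gives at 4.9. The illustrated values run from 0.61 down to 0.22, for differences of 3.9 and 2.45 points and SDs of 6.66 and 8. They assume an unadjusted t-test with all 30 patients per arm evaluable. It would go too far to say that power is known to be low, or that 0.80 is wrong for the placebo contrast, since the document lacks the SD needed to judge either.

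**What to change.** Keep n=60. In section VII.A, make these changes in one edit so that the section does not contradict itself:
- Delete the claim that the 4.9-point drug-placebo difference gives 0.80 power.
- Correct the d=0.5 sentence: 30 per arm gives a power of 0.48 at that effect.
- Remove the response-proportion table, or replace it with one for the two active arms.
- State that with 30 evaluable per arm and two-sided alpha 0.05, an unadjusted comparison has 0.80 power for a between-arm MADRS difference of about 0.74 SD (4.9 points if SD 6.66, 5.9 if SD 8, 7.4 if SD 10). Add that this is smaller with baseline adjustment (about 0.64 SD at a correlation of 0.5) and larger with dropout (about 0.83 SD with 24 per arm).

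The further power statement under VII.B, which refers to three groups of 20, does not fit a two-arm trial and should be reconciled at the same time.

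In section VII.C, name the adjusted between-arm MADRS difference with its 95% CI as the reported primary result, and state that P >= .05 will not be read as equal efficacy.

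The changes are wording only, with no added patients or procedures. The downside is a less favourable stated power.
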